### Aim 2/3: Behavioral Intervention

**Recruitment and training of peer health educators.** The study team has built strong AA community relationships from work on a prior funded DOD grant [Synergistic IDEA Award (#PC140667)]. Peer educators from this prior grant will be re-contacted to participate in the Peer Genetic Study. A total of five peer educators will be recruited. If prior peer educators are not available to commit to the study, additional avenues to recruit peer health educators will be through CityLife Clinics or MEE Productions, Inc. Men need not have previous health care experience to be trained as a peer educator. [name] or [name] will lead the educator training sessions. Culturally relevant issues will be addressed throughout the 9 training sessions, as they pertain to each of the training modules. Questions and concerns from peer health educators will also be addressed throughout the training. Peer educators will also complete human subjects training to be able to collect participant subject data during the intervention. Peer educators will attend training sessions in person, typically over the dinner meal, and will be compensated \$20/hour of training time.

**Development of genetic training materials.** Content of the training materials for peer educators will be adapted from ASCO's Practice Guideline Genetics Toolkit. The toolkit modules will be adapted as follows: (1) understanding hereditary cancer, (2) assessing hereditary cancer risk, (3) considerations of genetic testing and results, (4) management PCA and PCA screening based on genetic test results, (5) financial and ethical considerations of genetic testing, (6) cultural issues to address regarding genetic testing among AA males, (7) PCA risk and lifestyle modifications, (8) implications of genetic testing on family members, and (9) case scenarios. Based on input from the study team, MEE Productions, Inc. will develop print materials for the training sessions covering the aforementioned content.

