### **Study Intervention.**

*Intervention Arm:* Men who are randomized to the intervention arm will be invited to a peer health education session, either in-person or virtually. Eighty-eight of the 176 men will be randomized to this group, and we will host sessions that attract roughly 6-8 men at a session. Our previous experience conducting peer health education sessions found that 6-8 men was an ideal attendance level, as it allowed for interaction and discussion but did not feel overwhelming. Each session will be facilitated by two peer educators, who can share responsibilities and interact with each other. We expect to offer 12-15 sessions, or roughly 1-2 sessions per month. Sessions will be scheduled at various times of the day and days of the week, to accommodate men with varying schedules and commitments. Each peer educator will be compensated for 2 hours of time to run a session from start to finish, being compensated at \$20/hour.

First, the peer educator will introduce the topic of PCA, so that men understand the disease and how it relates to their health. The educator will lead a discussion regarding PCA risk, family history, PCA genetics, considerations of genetic testing, implications of genetic testing on family and self, and financial and ethical considerations. The discussion is meant to be interactive, with men sharing stories and experiences and peer educators answering questions and clarifying facts. All information will be delivered in a culturally appropriate manner by peer educators who are from the community they are serving. Immediately following the discussion, men will complete a post-survey to measure short-term changes knowledge about prostate cancer and genetic testing, thoughts about cancer, in decisional conflict about genetic testing, attitudes toward genetic testing, subjective norms about testing, and intentions to seek genetic testing. We will also get feedback on the peer-led session.

*Control Arm:* After providing informed consent and completing the baseline survey over the telephone or in-person, eighty-eight men will be randomized to this arm and each man will receive an educational booklet. It is expected that materials will be mailed within 24 hours of the

---

telephone call or provided to the participant in person. The information will cover PCA risk, family history, PCA genetics, considerations of genetic testing, implications of genetic testing on family, and financial and insurance considerations.

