**Endpoint Survey.** All men, regardless of study arm, will complete an endpoint survey. A member of the study team will call each participant two months after either attending a peer education session (intervention arm) or being mailed the educational print materials (control arm). Previous research shows that two months is an adequate amount of time to digest the material and act upon it, if desired. The majority of items on the baseline survey, except for the demographic information, will be repeated on the endpoint survey. Participants who are not reached by telephone will be contacted by mail and by email to attempt to retain the maximum number of participants over time.

**Participant Compensation.** Each man who participates in all study-related activities will receive \$50 over the course of the study. Men in the intervention group will receive \$25 for completing the baseline survey via the mail and \$25 for completing the endpoint survey over the telephone at two-months post-intervention. Men in the control group will receive \$25 in their mailed packet of materials after completion the baseline survey and an additional \$25 for completing the endpoint survey over the telephone at two-months post-intervention.

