## 9.2 Analysis Plans

**Decisional Conflict to Consider Genetic Testing.** All study variables, such as demographics, PCA knowledge, and outcome responses, will be summarized in tables with descriptive statistics or graphically in data plots at each time they are assessed along with changes in responses over time. We will investigate imbalances in these data for potential confounding of primary and exploratory endpoint analyses and investigate disparities and intervention effect modification in various subgroups of subjects. The primary outcome is decisional conflict regarding genetic testing assessed by the 4-item SURE scale. To compute a summary decisional conflict score, the Likert-scaled responses will be averaged across the SURE item responses provided by a subject completing at least 2 of the 4 questions. The change in decisional conflict scores between baseline and endpoint at 2-months will be calculated and group means for these changes compared between subjects randomized to receive control materials vs. those randomized to receive the peer health education intervention (i.e., by intention to treat). The significance of the difference will be evaluated at the 0.05 level using a two-sided Student's t-test. The assumptions for this test will be carefully evaluated. If the changes are substantially skewed, they will be summarized with group medians and evaluated for significant differences by the nonparametric Wilcoxon's rank sum test. If concerns arise over potential confounding from imbalances in baseline covariates, we will conduct a sensitivity analysis by applying analysis of covariance (ANCOVA) to adjust the comparison for baseline imbalances, including baseline decisional conflict scores.

**Descriptive and Exploratory Analyses.** Exploratory analyses will include estimating the proportion of AA men meeting the NCCN guidelines for genetic testing and computing a 95% confidence interval using the Clopper-Pearson exact method. Summary statistics and qualitative analyses will be used to assess the genetic counseling experience of those subjects accepting the offer for genetic counseling. Additional analyses will include estimating the intervention effect on genetic testing/counseling intentions and uptake, respectively, changes in attitudes toward genetic testing, and understanding of personal genetic test results using discrete variable tests, such as McNemar's test.

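### The primary t-test treats all men as independent, although the intervention arm is taught in 12-15 interactive group sessions; if sharing a session makes outcomes alike, the standard error is too small and the type I error exceeds 5%

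*Combined protocol and SAP*

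**What the plan says.** Men are randomised individually, 88 per arm. In the intervention arm (section 6, Study Intervention), "we will host sessions that attract roughly 6-8 men at a session", and "We expect to offer 12-15 sessions, or roughly 1-2 sessions per month". The format is a group conversation: "The discussion is meant to be interactive, with men sharing stories and experiences and peer educators answering questions and clarifying facts". Sessions share facilitators: "Each session will be facilitated by two peer educators", and, under Aim 2/3: Behavioral Intervention, "A total of five peer educators will be recruited". In the control arm, "each man will receive an educational booklet".

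The endpoint is an individual telephone survey two months after the session or the mailing (section 6, Endpoint Survey). Section 9.2 takes each man's change score and compares arm means by intention to treat: "The significance of the difference will be evaluated at the 0.05 level using a two-sided" Student's t-test. The Wilcoxon rank sum test replaces it if changes are skewed, and ANCOVA is a sensitivity analysis for baseline imbalance. Section 9.3 sizes the trial at 75 analysed men per arm with an ordinary two-sample t-test. Section 9.2 promises to check the test's assumptions, but the only remedy it names is for skewness.

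**The concern.** This is a partially nested design: men in one arm share a session and two facilitators, and men in the other share nothing. The t-test, the Wilcoxon test and the ANCOVA, as described, all assume independent men.

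The protocol's own rationale (section 1.1) is that hearing other members of a group changes a man's attitudes. If that happens, outcomes within a session are positively correlated and the intervention mean is less precise than the t-test supposes. The error is in precision, not in the estimate. False positives exceed 5%, split evenly between the tails, and the 95% interval covers too rarely whatever the true effect.

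**Working it through.** **Inputs.** From 9.3: difference 0.40, SD 0.76, two-sided 5%, 75 analysed per arm, about 15% attrition. From section 6: 12-15 sessions. Assumed, because the documents do not give them: ICC 0.02, 0.05 and 0.10; attendance 100% or 80%; SD 0.76 for the change score.

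**Reproducing the plan's figure.** With independent men, n per arm = 2 × (1.960 + 1.282)² × 0.76² / 0.40² = 75.9, or 76, against 75 stated. Noncentral-t power at 75 per arm is 89.3%, and 77 per arm are needed for 90%. For attrition, 176 × 0.85 = 149.6. So 9.3 is reproduced closely, but only with a design effect of 1.

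**Effect of sessions.** With m analysed men per session, the variance of the intervention mean is multiplied by 1 + (m − 1) × ICC; the control mean is unaffected. Hence

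true SE / t-test SE = √{[2 + (m − 1) × ICC] / 2}, and actual type I error ≈ 2 × [1 − Φ(1.96 / ratio)].

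Here m = 75/15 = 5.0 to 75/12 = 6.25. Example with 12 sessions and ICC 0.05: √[(2 + 5.25 × 0.05)/2] = √1.131 = 1.064; 1.96/1.064 = 1.843; type I error 6.5%.

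If 80% attend, 60 men share sessions and 15 do not. The added term becomes 0.8 × (m − 1) × ICC, with m = 60/15 = 4 to 60/12 = 5.

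| ICC | SE ratio, full attendance (15 / 12 sessions) | Type I error, formula | Type I error, simulated | Simulated, 80% attend |
|---|---|---|---|---|
| 0 | 1.00 / 1.00 | 5.0% / 5.0% | 5.0% / 5.0% | 5.0% / 5.0% |
| 0.02 | 1.020 / 1.026 | 5.5% / 5.6% | 5.5% / 5.5% | 5.2% / 5.3% |
| 0.05 | 1.049 / 1.064 | 6.2% / 6.5% | 6.1% / 6.4% | 5.6% / 5.9% |
| 0.10 | 1.095 / 1.124 | 7.4% / 8.1% | 7.3% / 8.2% | 6.4% / 7.0% |

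The simulation used normal outcomes with equal total SD in both arms and a session effect in attenders only (200,000 replicates per full-attendance setting). In the worst case 4.1 of the 8.2 points lie in the tail favouring the intervention.

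**Other planned tests (simulated, full attendance, ICC 0.02 / 0.05 / 0.10).** Wilcoxon: 5.5% / 6.2-6.3% / 7.2-8.1%. ANCOVA: 5.7-5.8% / 6.6-6.9% / 8.2-9.1%. ANCOVA is worse because the ICC is defined on the change score. At an assumed baseline-endpoint correlation of 0.5, adjustment cuts the residual variance to 0.75 of the total and leaves the session variance intact, so the session share rises to ICC/0.75.

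**A session-robust test.** A bias-reduced cluster-robust SE (CR2) with Satterthwaite degrees of freedom (38 for 12 sessions, 47 for 15) held 4.9-5.2% in every setting, including uneven sessions of 2-9 men. The same SE for ANCOVA gave 5.2-5.8% at ICC 0.05 and 0.10 (2,500 replicates).

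**Power for 0.40, full attendance, ICC 0 / 0.02 / 0.05 / 0.10.** Planned t-test: 89% / 89% / 88% / 87%. Robust test: 88% / 86-87% / 84-85% / 80-82%. These use SD 0.76 for the change, which equals the score SD in 9.3 only at correlation 0.5, because SD of change = 0.76 × √[2(1 − r)]. At r = 0.3 (SD 0.90) the planned t-test has 77%; at r = 0.7 (SD 0.59) it has 98.5%.

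**The case against.** The strongest reply is that the effect may be negligible. No ICC is given, and the outcome is an individual call two months after the session. At ICC 0.01 the formula gives only 5.2-5.3%. Men who never attend are analysed by intention to treat and are not clustered. The session count is only an expectation: at 1-2 a month, 12-15 sessions take 6-15 months, against 3.5 years of enrolment in the Study Summary. With 22 sessions (assumed) the type I error would be 5.3% / 5.7% / 6.4%. All of this stands. It limits the size but does not show that the ICC is zero.

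A finer point also stands. If session and booklet gave every man the same outcome, sessions would add no variance and the t-test would keep its level. Similar men merely choosing the same session would not by themselves inflate the error either. The inflation needs sessions that truly differ in effect. That is plausible against an active control, and the interval is then too narrow at any true effect.

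The promise to check assumptions helps little, because every named alternative assumes independence too.

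Finally, power depends more on the unstated SD of the change score than on clustering. Section 6 also describes SURE as four Yes/No items, whereas 9.2 averages Likert responses. The power figures are therefore conditional on the scale and SD in 9.3.

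**Conclusion.** The concern holds as a conditional statement: if sharing a session induces an ICC above 0, the planned standard error is too small and the type I error exceeds 5%. The excess is about half a point at ICC 0.02, 1 to 1.5 points at 0.05 and 2 to 3 points at 0.10 with full attendance, and less with non-attendance or more sessions. These ICCs are assumptions. The estimate is unbiased, and at ICC 0 the t-test is valid. The power claim in 9.3 is a smaller, separate matter: 89.3% rather than 90% even without clustering, if the change score has SD 0.76. This should be fixed because the remedy is cheap, and session membership is hard to reconstruct if it is not recorded.

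**What to change.** **Section 9.2.** Keep the intention-to-treat difference in mean change as the estimate. Base its p-value and 95% interval on a CR2 standard error with Satterthwaite degrees of freedom, with each session as one cluster and each control and each non-attender as his own cluster. Use the same SE for the ANCOVA and, if changes are skewed, for the difference in mean ranks in place of the plain Wilcoxon test. A mixed model with a session intercept in the intervention arm only is acceptable if its slight reweighting towards non-attenders is stated.

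**Data collection.** Record the session ID and both educator IDs. Add a sensitivity analysis with a session intercept and a multiple-membership educator effect, and state that the primary test applies to these five educators.

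**Section 9.3.** Replace the claim of 90% power or more with the robust test's power at 75 per arm over ICC 0-0.10, and state the SD assumed for the change score.

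**Cost.** Wording and three ID fields. The interval is slightly wider; at ICC 0 power falls from about 89% to 88%. If men in a session are alike only because similar men chose it, the robust interval is wider than needed. A session-only SE does not cover educators treated as random: with session and educator each holding an assumed 2.5% of the variance, its type I error is about 8.5%, against about 6% for the educator model with 15 sessions. Five educators estimate that variance poorly, which is why it belongs in a sensitivity analysis. No added enrolment is proposed.

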**Referral to Genetic Counseling.** Men from both groups who decide they want to proceed with genetic counseling and genetic testing will be given the number to contact the Cancer Risk and Genetics Program at Sidney Kimmel Cancer Center at Jefferson, led by [name] (study PI). Once men contact the Genetics Program, an intake will be performed to determine if they meet personal or family history criteria for genetic testing. Current NCCN criteria for PCA genetic testing include any of the following: (1) personal history of advanced or metastatic PCA, (2) family history of brother, father, or multiple family members diagnosed with PCA at age <60, (3) first-degree, second-degree, or third-degree relatives with cancers of the breast, ovary, prostate, pancreas, colon, or endometrium suggestive of a hereditary cancer syndrome. Men will then be scheduled for a genetic counseling visit to formally cover information regarding genetic testing such as how cancers can be inherited, types of genetic test results, and implications for the man and his family. Once the man agrees to proceed with testing, a saliva sample will be collected and sent to Invitae, a CLIA-certified and experienced clinical genetic testing laboratory to perform multigene testing. Genes to be tested by sequencing and deletion/duplication testing will include *BRCA1*, *BRCA2*, *ATM*, *PALB2*, *CHEK2*, *NBN*, the DNA mismatch repair genes, and additional genes as needed. Invitae follows ACMGG guidelines for variant classification and all standard procedures for variant reclassification updates. Since men in this study may be underinsured, the study will pay for the cost of genetic testing for all men who undergo genetic counseling. Once

---

results return, men will be called to come in for a results disclosure visit to discuss their results and answer any questions.

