**Assessment of genetic counseling experience.** Since genetic testing of AA men is a novel field and is understudied, we will take the opportunity to survey men about their genetic counseling experience at the pre-test counseling visit and the post-test visit. We will use the Satisfaction with Genetic Counseling Scale, a 6-item validated measure with responses entered on a Likert scale ranging from “Strongly Agree” to “Strongly Disagree”. The questions include: (1) The provider or staff member seemed to understand the stresses I was facing; (2) The provider or staff member helped me to identify what I needed to know to make decisions about genetic testing; (3) I feel better about my health after meeting with this provider or staff member; (4) The session was about the right length of time I needed; (5) The provider or staff member was truly concerned about my well-being; and (6) The session was valuable to me.

At the post-test visit, we will also administer a survey developed regarding knowledge and understanding of genetic test results, which has previously been published by the study team in a male population undergoing genetic testing. This survey includes questions about the man’s genetic test results (“I was found to carry a genetic mutation” or “I was found to carry a variant of uncertain significance”), interpretation of the results (“I am at higher risk for PCA based on my genetic result” or “My children are recommended to be tested based upon my genetic result”), and sharing of genetic results with family and providers.

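### Understanding of personal genetic test results is listed for an intervention effect and a McNemar-type test, but it is measured once and only in men who chose testing after randomisation

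*Combined protocol and SAP*

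**What the plan says.** Section 9.2, in the paragraph on descriptive and exploratory analyses, gives one list of further work: "estimating the intervention effect on genetic testing/counseling intentions and uptake, respectively, changes in attitudes toward genetic testing, and understanding of personal genetic test results". The sentence closes by naming discrete-variable tests, with McNemar's as the example.

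Section 6 shows how that last outcome arises:

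- **Timing.** Under Assessment of genetic counseling experience: "At the post-test visit, we will also administer a survey developed regarding knowledge and understanding of genetic test results". No other administration is described. The baseline and two-month surveys cover general knowledge of prostate cancer genetics, not a man's own result.
- **Content.** "This survey includes questions about the man’s genetic test results", their interpretation, and sharing them with family and providers. The outcome does not exist for a man without a result.
- **Who gets there.** The paragraph on referral states: "Men from both groups who decide they want to proceed with genetic counseling and genetic testing will be given the number to contact". That number belongs to the genetics programme. Then "an intake will be performed to determine if they meet personal or family history criteria for genetic testing", followed by a counselling visit. Finally, "Once the man agrees to proceed with testing, a saliva sample will be collected", and the man is called back for disclosure.

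In 9.2, intention to treat is stated for the primary comparison only. The sentence just before the one at issue restricts the counselling-experience analysis to men who accept counselling, and uses summary statistics and qualitative analysis.

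**The concern.** Deciding to proceed, calling the programme and agreeing to testing all come after randomisation, and the plan expects that peer education may change them. The tested men in the two arms are then subsets chosen by a process that may differ by arm, so they need not be alike in health literacy, motivation or prior knowledge. All of them have also had professional counselling before they answer.

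If peer education brings in men who are more hesitant or less well informed, understanding among tested intervention men could look poorer than among the fewer tested controls, although the intervention changed no man's understanding. A success in reaching men could be reported as a failure in understanding.

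The named test is a separate problem. McNemar's test compares paired binary responses. This outcome has no baseline to pair with, and the two arms are independent groups.

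**Working it through.** **The plan's own figures.** No sample size, power or expected rate is given for this analysis. Section 9.3 sizes only the primary outcome. Its 75 per group reproduces closely (76 by the normal approximation for a difference of 0.40, SD 0.76, 90% power, two-sided 5%), but nothing here depends on it. From the documents come 88 men randomised per arm and 75 per arm expected for analysis. All uptake and understanding rates below are assumptions.

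**Step 1: a hand illustration.** Assume that 9 of 88 controls (10%) and 26 of 88 intervention men (30%) are tested. Assume that the 9 readiest men in either arm understand their result with probability 0.85, and the 17 additional intervention men with probability 0.65. No man's understanding depends on his arm.

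- Control: 0.85.
- Intervention: (9 × 0.85 + 17 × 0.65) / 26 = (7.65 + 11.05) / 26 = 18.70 / 26 = 0.719.
- Apparent effect: 0.719 − 0.85 = −0.13.
- 95% half-width: 1.96 × √(0.85 × 0.15/9 + 0.719 × 0.281/26) = 0.29.
- Probability that a two-sided Fisher exact test at 0.05 rejects in this setting: about 4%.

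The estimate is displaced by 13 points, but the test does not reject more often than its nominal level.

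**Step 2: a range of assumptions.** Take 75 men per arm and a latent trait, such as health literacy, that raises the log-odds of a correct answer by 1 per SD (58% correct overall). The arm has no effect on understanding. The slope is the log-odds of uptake per SD of the trait. Rejection is for a two-sided test of two proportions at 5%.

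| Uptake, control vs intervention | Slope, control / intervention | Understanding among tested, control vs intervention | Difference (points) | Rejection |
|---|---|---|---|---|
| 20% vs 40% | 0 / 0 | 58.2% vs 58.2% | 0 | 5% |
| 20% vs 20% | 1 / 1 | 71.8% vs 71.8% | 0 | 5% |
| 20% vs 40% | 1 / 1 | 71.8% vs 68.3% | −3.5 | 5.5% |
| 20% vs 40% | 1 / 0.3 | 71.8% vs 61.7% | −10.0 | 9.7% |
| 20% vs 40% | 1 / 0 | 71.8% vs 58.2% | −13.6 | 13.7% |
| 10% vs 50% | 1.5 / 0.5 | 78.7% vs 63.0% | −15.7 | 9.0% |

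The first two rows show that the bias is conditional. It vanishes when uptake is unrelated to the trait, or when selection is the same in both arms. The third row shows that doubling uptake with the same dependence on the trait moves the estimate little. Differences of 10 points or more appear here only where the dependence also differs by arm. At 75 men per arm, uptake of 20% and 40% means about 15 and 30 tested men.

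**Step 3: a composite over all randomised men.** Score tested-and-understood as yes and every other man as no. In the Step 1 setting this gives 7.65/88 = 8.7% against 18.70/88 = 21.3%. Randomisation protects this comparison, but here the whole difference comes from uptake, so it must be read as a combined effect.

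**The case against.** **The sentence can be read differently.** The word respectively in 9.2 could close the phrase about an intervention effect after intentions and uptake. Attitudes and understanding would then be separate analyses, and the paired test named gives this some support. The reading is possible but does not rescue the sentence: understanding would still be assigned to tests such as McNemar's with no second measurement to pair.

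**The item is minor.** It is the last in a list of additional exploratory analyses. Section 9.1 has one hypothesis, on decisional conflict, and the exploratory outcomes named in 2.1 do not include understanding of personal results. This stands and limits the importance of the point.

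**The plan has safeguards.** Section 9.2 will look for imbalances affecting exploratory endpoints too, baseline knowledge and intentions are collected, and 9.3 considers multiple imputation and pattern mixture models. Baseline data could support an adjusted analysis, but no method is stated for selection into testing. Imputation does not help when the missing quantity, a man's understanding of a result he never had, does not exist.

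**The numbers are assumed and imprecise.** This also stands. A reader might infer from the 13-point illustration that false positives would be common. The calculation does not support that: rejection there is about 4%, and the half-width of 29 points is over twice the bias. A reader might also expect bias in either direction, but every non-zero setting worked here makes the intervention look worse.

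**Conclusion.** The point holds as a conditional estimation bias in an exploratory analysis, together with a test that does not fit the data. An arm difference among tested men cannot be taken as an effect of the randomised intervention without strong assumptions about who gets tested. With no true effect, the spurious difference is 0 to about 16 points across the assumed settings, with rejection rates from about 4% to 13.7%. It would usually go undetected with so few tested men, but it would still distort the reported estimate. The primary analysis is untouched.

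Two stronger readings are not supported. A reader might infer that no arm effect involving this outcome can be obtained from the data; the composite in Step 3 can be, although the plan does not specify it. A reader might also infer that men who fail the history criteria at intake are excluded from testing. Section 6 says that the criteria are checked and that men are then scheduled for counselling. It does not say what happens to men who do not meet them, so the argument rests on each man's own choices after randomisation.

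**What to change.** In 9.2, remove understanding of personal genetic test results from the list of intervention effects and from the clause naming McNemar's test. Report it descriptively among tested men: number and proportion with an exact confidence interval, shown by arm for information, with no test between arms and no effect claim. This matches the descriptive treatment 9.2 already gives to counselling experience.

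If an arm effect is wanted, define a composite for all 176 randomised men: tested and understood the result, with untested men counted as no. Interpret it as a combined effect on uptake and understanding. Section 9.2 gives no scoring rule for this survey, so the definition of understood should be fixed in advance, with a rule for tested men who lack the post-test survey.

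The cost is a sentence or two in 9.2 and no new data collection. What is lost is an exploratory comparison that would need strong, untested assumptions to interpret.
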